3.1.2 Data included in analyses before the completion of the study

An interim analysis will be performed after the first 30 patients enrolled have completed at least 4 cycles of treatment with LDK378 or have discontinued earlier. For the interim analysis, all data from patients on or before the interim analysis cut-off date will be used.

The primary CSR will be produced after all patients have undergone at least 24 weeks (6 cycles) of treatment with LDK378 or have discontinued earlier. All available data from all patients up to this cutoff date will be analyzed. Only data with an assessment date or event start date (e.g. vital sign assessment date or start date of an adverse event) prior to or on the cut-off date will

be included in each analysis. (Example: If the cut-off date is e.g. 15-Oct-2011, an AE starting on 13-Oct-2011 will be reported, whereas an AE with a start date on 17-Oct-2011 will not be reported).

3.1.3 Analysis sets

A patient is considered to be enrolled into the study if they have signed the study informed consent. Only patients who have signed study informed consent prior to study procedures will be included in the analysis data sets.

Full Analysis Set

The Full Analysis Set (FAS) consists of all patients who receive at least one dose of LDK378. Unless otherwise specified the FAS will be the analysis set used for all analyses and listings.

Efficacy Analysis Set (Interim analysis only)

The Efficacy Analysis Set (EAS) is used in the interim analysis for the analysis of tumor response data based on investigator assessments. It is a subset of the FAS, and consists of patients who received the first dose of LDK378 at least 16 weeks prior to the analysis cutoff date. The EAS will be the primary data set used in interim analysis for the analysis of tumor response data (ORR and DOR based on investigator assessments).

Safety Set

The Safety Set consists of all patients who receive at least one dose of LDK378. All safety data will be analyzed using the Safety Set.

The FAS and Safety Set in this study are identical.

Per-Protocol Set

The Per-Protocol Set (PPS) will consist of a subset of patients in the FAS who are compliant with requirements of the Clinical Study Protocol (CSP). The PPS consists of patients who have an adequate tumor assessment at baseline, a follow-up tumor assessment >7 weeks after starting treatment (unless disease progression is observed per investigator's assessment before that time), and no major protocol deviations. PPS will be used in the supportive analysis of ORR.

The major protocol deviations that will lead to removal of patients from the PPS are listed below:

- No confirmation of ALK positive status by the Abbott Molecular Inc FDA-approved FISH assay or by the CFDA approved IHC Ventana test prior to first dose. Patient has a histologically or cytologically confirmed diagnosis of NSCLC that is not ALK positive as assessed by the Abbott Molecular Inc FDA-approved FISH assay or by the CFDA approved IHC Ventana test.
- No histological or cytological diagnosis of NSCLC
- Neither Stage IIIB nor IV NSCLC
- WHO performance status equal to 3 or 4 at screening

- No prior treatment with crizotinib
- Prior treatment with crizotinib with no noted PD during or after crizotinib treatment OR prior treatment with crizotinib discontinued due to toxicity
- Patient has been previously treated with more than 2 lines of chemotherapy prior to study entry
- No documentation of disease progression at study enrollment
- No measurable lesion from RECIST 1.1 evaluation at baseline per investigator assessment. For analysis by BIRC assessment based on PPS, 'No measurable lesion at baseline' is based on BIRC assessment per RECIST 1.1.
- RECIST lesions previously been irradiated has been chosen as target lesions without a clear progression since irradiation
- Patient has received an ALK inhibitor investigational agent (except Crizotinib) before first dose of study treatment.
- Patient has a history of carcinomatous meningitis
- Patient with symptomatic central nervous system (CNS) metastases neurologically unstable or has required increasing doses of steroids within the 2 weeks prior to study entry.

Pharmacokinetic Analysis Set

The Pharmacokinetic Analysis Set (PAS) consists of all patients who received at least one dose of LDK378 and have at least one evaluable PK sample.

Depending on whether the sample is part of a full profile or a sparse sample, the specific criteria are listed as follows.

A sparse PK sample is considered to be evaluable if:

- The patient takes study drug according to the original assigned dose for at least 5 consecutive days without interruption or dose modification prior to the PK sampling day (except for PK run-in Day 1 for patients with extensive assessment and Cycle 1 Day 1), AND
- On the PK collection day, the patient takes study drug according to the originally assigned dose,
- Vomiting doesn't occur within 6 hours following the last dose intake prior to the PK sample draw, AND
- For the pre-dose sample, draw occurs between 18 to 30 hours after the last dose intake (except for PK run-in Day 1 for patients with extensive assessment and Cycle 1 Day 1), and
- For the pre-dose sample, the draw occurs before the next dose intake, and
- A sample can be considered to be not evaluable as per scientific judgment of the clinical pharmacology expert

An evaluable full PK profile is defined as:

CONFIDENTIAL - For Business Use Only

- The patient takes study drug according to the original assigned dose for at least 5 consecutive days without interruption or dose modification prior to the PK sampling day (except for PK run-in Day 1 for patients with extensive assessment and Cycle 1 Day1), AND
- No vomiting occurs within 6 hours following the last dose intake prior to the PK sample draw, AND
- On the PK collection day, the patient takes study drug according to the originally assigned dose, AND
- Additionally, an entire profile can be considered non-evaluable as per scientific judgment of the clinical pharmacology expert even if the above criteria are fulfilled. Reason will be documented in the merged PK datasets.

Any blood samples missing blood collection date or time, or missing associated study drug dosing date or time will be excluded.

Frequency counts and percentages (using FAS as denominator) of patients in each of the above defined analysis sets will be summarized. In addition, listings of patients included in each of the analysis sets will be provided.

3.1.4 Classification into Analysis Sets

Patients were excluded from the analysis populations defined above based on the protocol deviations entered in the database and/or on specific subject classification rules, see [Table 3-1](#) below.

Table 3-1 Patient classification rules

Analysis Population	Patient classification rules leading to exclusion
Full Analysis Set	Patients who did not receive at least one dose of study drug
Efficacy Analysis Set (Interim analysis only)	Patient did not receive at least one dose of LDK378 OR First dose of LDK378 < 16 weeks prior to data cut-off
Safety Set	Patients who did not receive at least one dose of study drug.
Per Protocol Set	Protocol deviations that will lead to removal of patients from Per Protocol Set, i.e. INCL01, INCL02, INCL03, INCL04, INCL07, INCL08, INCL09, INCL10, INCL11, INCL12, INCL13, INCL33, EXCL02, EXCL03, EXCL04 Patient who do not have an adequate tumor assessment at baseline, or a follow-up tumor assessment > 7 weeks after starting treatment (unless disease progression is observed before that time). For PPS (inv.) patients with no target lesions at baseline per investigator are excluded; for PPS (BIRC) patients with no target lesions at baseline per BIRC are excluded.
Pharmacokinetic analysis set	Patients who do not have at least one evaluable PK sample

All protocol deviations and subject classification rules will be finalized before database lock.

CONFIDENTIAL - For Business Use Only

Below lists handling of some special cases in analysis set classification:

- If informed consent is not properly obtained from the patient (signed and dated prior to any study related procedures), data from the patient will be excluded from all analysis populations including table summaries and listings.
- If a patient withdraws consent (based on ‘Was informed consent withdrawn’ is ‘Yes’ for study informed consent in the “Withdrawal of informed consent” page)
 - If consent withdrawal date is before start of treatment date, or start of treatment date is missing, then patients’ data will not be included into any analysis.
 - If consent withdrawal date is after start of treatment date, then all data collected before withdrawal will be included in the analysis, and data collected after consent withdrawal will be excluded from the date of withdrawal by programming cut-off.
- If a patient does not meet inclusion/exclusion criteria:
 - If patient is not treated, then the patient data will be listed in screening failures (see [section 3.2.2](#))
 - If patient is treated, then the patient data will be included in FAS and safety set, but might be excluded from PPS depending on whether this violation is a major protocol deviation or not.

3.1.5 General statistical methodology

3.1.5.1 Multiple assessments within post-baseline visits

If there are multiple measurements/samples within the same post-baseline visit, the last measurement/sample within the visit (sorted by date and as available by time or repeat measurements) will be used in the analysis by visit or overall. For any analyses regarding abnormal assessments or analyses based on worst (or best in the case of ECOG status) post-baseline value (laboratory, ECGs, vital signs, ECOG performance status), all post-baseline values will be included (scheduled, unscheduled, repeat). For any other analyses, only scheduled visits will be included. All unscheduled and repeat measurements will be included in listings.

Laboratory Data

For laboratory data, assessments can be collected from both local and central laboratory on the same date. For shift tables using Common Terminology Criteria (CTC) v4.03 grades to compare baseline to the worst post-baseline value, the assessment with worst post-baseline value is used for analyses irrespective of the source. For Liver function test (LFT) summaries, where concurrent measurements are used in the calculation of number and percentage of patients with worst post-baseline values, the assessment with worst post-baseline value is used (since worst values are based on the largest ratio of lab value to its ULN for each patient) although the worst values for the different parameters may be coming from different laboratories.

12-lead ECG assessments

For all patients, triplicate ECGs are targeted to be measured at the protocol-defined (nominal) time-points. If any patient had more than one measurement at a specific time point, the average of all available measurements (only scheduled one) associated with the nominal time point will be used for the analyses.

3.1.5.2 Center pooling

Center effects will not be analyzed and the main analyses will therefore be conducted with the pooled datasets.

3.2 Statistical methods used in reporting

3.2.1 General presentation of descriptive summaries

Qualitative data (e.g., sex, race, etc.) will be summarized by frequency count and percentages. Percentages are calculated using the number of patients in the relevant population as the denominator.

Quantitative data (e.g., age, body weight, etc.) will be summarized by appropriate descriptive statistics (i.e. mean, standard deviation, median, minimum, and maximum).

Summary statistics for PK concentrations and PK parameters include the following unless otherwise specified: n, mean, SD, coefficient of variation (CV) for mean, geometric mean, CV% for geometric mean, median, minimum and maximum.

3.2.2 Patient demographics and other baseline characteristics

The FAS will be used for all patient demographic and baseline characteristic summaries and listings, unless otherwise specified.

Basic demographic and background data

All demographic and baseline disease characteristics data will be summarized and listed. Categorical data (e.g. sex, age groups: <65 and ≥65 years, race, ethnicity, WHO performance status, smoking history) will be summarized by frequency counts and percentages. Continuous data (e.g. age, weight, height, and Body Mass Index (BMI)) will be summarized by descriptive statistics. Height is collected only once in the study. Baseline weight is the last non-missing value observed before the first administration of study drug. BMI will be calculated using height and baseline weight:

$$\text{BMI (kg/m}^2\text{)} = \text{weight [kg]} / (\text{height [m]})^2$$

Patient demographic characteristics will be summarized by quartile of average SS Ctrough using Pharmacokinetic Analysis Set (see [Section 3.2.8](#))

Diagnosis and extent of cancer

Descriptive statistics and frequency counts and percentages will be tabulated, as appropriate, for diagnosis and extent of cancer based on the data collected on the eCRF including primary site of cancer, details of tumor histology/cytology, histological grade, stage at initial diagnosis, stage at time of study entry, time (in months) since initial diagnosis of primary site, time (in

months) from initial diagnosis to first recurrence/progression, time (in months) since most recent relapse/progression, current extent of disease (metastatic sites), number of metastatic sites at baseline, types of lesions (target and non-target lesions) at baseline, number of target lesions at baseline, and disease burden at baseline for target lesion (based on the data collected on the RECIST eCRF page).

Medical history

Medical history and ongoing conditions, including cancer-related conditions and symptoms will be summarized and listed. Separate summaries will be presented for ongoing and historical medical conditions. The summaries will be presented by primary system organ class (SOC) and preferred term (PT). Medical history and current medical conditions are coded using the latest Medical Dictionary for Regulatory Activities (MedDRA) terminology prior to database lock.

Prior anti-cancer therapy

Prior anti-neoplastic (anti-cancer) therapy will be listed in three separate categories: 1. medications, 2. radiotherapy, and 3. surgery.

The number and percentage of patients who received any prior anti-neoplastic medications, prior anti-neoplastic radiotherapy or prior anti-neoplastic surgery will be summarized.

All patients must have received crizotinib for inclusion in the study; reason for crizotinib discontinuation, best response on crizotinib, duration of best response, and time from start of last crizotinib treatment to progression (date of progression on crizotinib - start date of last crizotinib + 1) will be summarized.

Prior anti-neoplastic medications will be summarized by chemotherapy (medication) setting, other therapy (medication) setting, number of prior regimens of chemotherapy. Prior antineoplastic medications will also be summarized by Anatomical Therapeutic Chemical (ATC) class and PT using the latest WHO drug dictionary prior to database lock.

The summary of prior anti-neoplastic radiotherapy will include a summary of radiotherapy locations and settings at last radiotherapy.

The summary of prior anti-neoplastic surgery will include the time between the last surgery to start of treatment, procedure at last surgery and residual disease at last surgery.

Screening phase disposition

Patients who sign an informed consent but fail to be started on treatment for any reason will be considered a screening failure. These patients are not treated with study drug. Frequency counts and percentages will be tabulated for all patients as follows:

- Number (%) of patients who completed screening phase (based on the presence of study phase completion date/ "subject status" is checked as "completed" and the 'Next phase entered' is 'Treatment' or 'Treatment run-in' in the 'Screening Phase Disposition' page);
- Number (%) of patients who discontinued during screening phase (based on the presence of date of discontinuation and discontinuation / "subject status" reason entered and 'Will the subject continue into the next phase of the trial' is 'No' in the 'Screening Phase Disposition' page);

- Reasons for screening phase discontinuation (based on reasons recorded in Screening Phase Disposition' page)

All screen failure patients with reasons for screen failure will be listed and summarized by criteria.

3.2.3 Protocol deviations

Frequency counts and percentages of patients in the FAS with any CSR-reportable protocol deviations (related to study inclusion/exclusion criteria, conduct of the trial, patient management or patient assessment) will be tabulated by the deviation category. Major protocol deviations will be tabulated separately.

All protocol deviations will be listed.

3.2.4 Patient disposition

The FAS will be used for the patient disposition summary tables and listings. The following will be tabulated.

Relating to treatment phase:

- Number (%) of patients entered “Treatment run-in” (PK run-in) phase
- Number (%) of patients entered “Treatment” phase
- Number (%) of patients who are still on treatment (based on the absence of the ‘End of Treatment Phase Disposition’ page);
- Number (%) of patients who discontinued treatment (based on completion of the ‘End of Treatment Phase Disposition’ page with date of discontinuation and reason of discontinuation/ ‘Subject Status’ entered);
- Number (%) of patients who entered post-treatment follow-up phase from treatment phase (based on ‘Next Phase Entered’ is ‘Post-treatment follow-up’ on the ‘End of Treatment Phase Disposition’ page for patients who discontinued treatment);
- Number (%) of patients who entered survival follow-up from treatment phase (based on ‘Will subject continue into the next phase of the trial’ is ‘No’ and ‘Will the subject be followed for survival’ is ‘Yes’ on the ‘End of Treatment Phase Disposition’ page for patients who discontinued the treatment);
- Number (%) of patients who discontinued from study from treatment phase (based on ‘Will subject continue into the next phase of the trial’ is ‘No’ and ‘Will the subject be followed for survival’ is ‘No’ on the ‘End of Treatment Phase Disposition’ page for patients who discontinued the treatment);
- Primary reasons for treatment discontinuation (based on discontinuation reasons entered under ‘Subject Status’ in the ‘End of Treatment Phase Disposition’ page);

Relating to the post-treatment follow-up phase:

- Number (%) of patients who are still in the post-treatment follow-up phase (based on presence of the ‘End of Treatment Phase Disposition’ page and absence of the ‘End of Post-treatment Phase Disposition’ page);

- Number (%) of patients who discontinued from the post-treatment follow-up phase (based on completion of 'End of Post-treatment Phase Disposition' page with date of discontinuation and discontinuation reasons entered under 'Subject Status');
- Number (%) of patients who entered survival follow-up from post-treatment phase (based on completion of 'End of Post-treatment Phase Disposition' page with date of discontinuation and discontinuation reasons entered under 'Subject Status' and 'Will the subject be followed for survival' is 'Yes' for patients who discontinued from the post-treatment follow-up phase);
- Number (%) of patients who discontinued from study (based on completion of 'End of Post-treatment Phase Disposition' page with date of discontinuation and discontinuation reasons entered under 'Subject Status' and 'Will the subject be followed for survival' is 'No' for patients who discontinued from the post-treatment follow-up phase);
- Primary reasons for discontinuation from the post-treatment follow-up phase (based on discontinuation reasons entered under 'Subject Status' in the 'Post-treatment Phase Completion' page).

3.2.5 Study treatment

Duration of exposure to study drug, cumulative dose, average daily dose, DI and RDI (including categories: <50%, 50%-<75%, 75%-<90%, 90%-110%, ≥110%) will be summarized. In addition, the duration of exposure to study drug will be categorized into time intervals; frequency counts and percentages of patients with exposure in each time interval will be presented. The number of patients with dose changes, reductions and interruptions, and the corresponding reasons will be presented.

Time to first dose reduction and time to first dose interruption will be presented graphically using Kaplan-Meier methodology. Patients who did not have a dose reduction will be censored at the date of the last dose of study drug. Summary statistics of time to first dose reduction/interruption will be presented for patients with at least one dose reduction/interruption.

All information relevant to drug administration will be listed using safety set.

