Data analysis	Using the PAS, PK concentration versus time profiles of LDK378 will be summarized separately for patients with extensive PK assessment and patients with sparse PK sampling. The mean and individual concentration versus time profiles of LDK378 will be displayed graphically for full PK profile and trough collections. LDK378 PK parameters, including but not limited to AUClast, AUC0-24h, AUCinf, Cmax, Tmax, Lambda z, terminal T1/2, T1/2,acc, Racc, CL/F (or CLss/F at steady state) and Vz/F, as appropriate will be derived from PK run-in patients with extensive PK assessment. All PK parameters will be summarized. The PK parameters and concentration data will be listed Safety data including adverse events, vital signs, ECG and laboratory abnormalities will be summarized and listed. For efficacy, ORR as assessed by investigator will be estimated and the binomial exact 95% CI provided. DOR will be listed by patient and described using Kaplan-Meier methods and relevant statistics. DCR will be estimated and the binomial exact 95% CI provided. PFS, and OS will be described using Kaplan-Meier methods and appropriate summary statistics. Efficacy data will be listed. [REDACTED] [REDACTED] [REDACTED]
Key words	ALK, NSCLC, LDK378

Amendment 3

Amendment rationale

As of 29-Sep-2015, of 103 patients treated, 66 patients have been discontinued from treatment and 37 are still receiving study treatment.

The amendment provides follow up evaluations for hepatic toxicities and work-up guidelines for potential Drug Induced Liver Injury (DILI) cases in order to optimize patient safety.

Other change was implemented in this amendment: Dose guidance modification for QTc text is being updated to provide clarification on monitoring procedure.

Changes to the protocol

Changes to specific sections of the protocol are shown in the track changes version of the protocol using strike through red font for deletions and red underlined for insertions.

The following sections to the protocol were changed:

- List of abbreviations updated with commonly used abbreviations
- Table 6-3: “Refer to Section 6.2.4.2 for additional follow-up” was added for AST or ALT and concurrent Total bilirubin management. Follow-up description updated for Grade 3 QTc interval prolonged.
- Section 6.2.4.2: Updated on following up evaluations for hepatic toxicities and work-up guidelines for potential Drug Induced Liver Injury (DILI) cases to align with Novartis Oncology trial standard language.

IRB/IEC

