Dose reductions due to AEs occurred in 58.4% of patients treated with LDK378 at the 750 mg dose; 38.8% of patients had only 1 dose reduction. The most frequent AEs requiring dose adjustments or interruptions reported in $\geq 5\%$ of the patients were: ALT increased, nausea, AST increased, vomiting, diarrhea, fatigue, and abdominal pain. Adverse events (AEs) leading to study drug discontinuations occurred in 10.2% of patients treated with LDK378 at the 750 mg dose. The most frequent AEs leading to study drug discontinuations were decreased appetite, pneumonia, ALP increased, pneumonitis, and respiratory failure.

Serious adverse events (SAEs) reported in 2% or more of the 255 patients treated at the recommended dose of 750 mg were convulsion, pneumonia, interstitial lung disease (ILD)/pneumonitis, dyspnea, hyperglycemia, and nausea. Fatal adverse reactions occurred in

5% of patients, consisting of: pneumonia (4 patients), respiratory failure, ILD/pneumonitis, pneumothorax, gastric hemorrhage, general physical health deterioration, pulmonary tuberculosis, cardiac tamponade, and sepsis (1 patient each). Adverse events of special interest to be monitored for ceritinib have also been identified and include: hepatotoxicity, interstitial lung disease/pneumonitis, QT interval prolongation, bradycardia, hyperglycemia gastrointestinal toxicity (nausea, vomiting and diarrhea) and pancreatitis (including lipase and amylase elevations). For additional details, refer to [Investigator's Brochure].

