10.5.3.5 Tolerability

[figure not shown]
Tolerability will be summarized in terms of dose reductions or drug interruption due to an AE.

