3.1.1.2 Date of first/last administration of study drug

The date of first administration of study drug is defined as the first date when a non-zero dose of study drug is administered and recorded on the Dosage Administration Record (DAR) electronic Case Report Form (eCRF). For the sake of simplicity, the date of first administration of study drug will also be referred as start date of study drug.

The date of last administration of study drug is defined as the last date when a non-zero dose of study drug is administered and recorded on the DAR eCRF. This date is also referred as last date of study drug.

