4.1.2.8 Incomplete dates for last dose of study drug

Scenario 1

If the last date of study drug is after the cut-off date or is completely missing and there is no end of treatment eCRF page and no death date the patient should be considered to be on-going and use the cutoff date for the analysis as the last dosing date

Scenario 2

If the last date of study drug is completely or partially missing and there is EITHER an end of treatment eCRF page OR a death date available then imputed last dose date:

- = 31DECYYYY, if only Year is available and Year < Year of min (EOT date, death date)
- = Last day of the month, if both Year and Month are available and Year = Year of min (EOT date, death date) and Month < the month of min (EOT date, death date)
- = min (EOT date, death date), for all other cases

The imputed date will be compared with start date of study drug.

If the imputed date < start date of study drug, then last date of study drug is set to start date of study drug;

Otherwise, use the imputed date.

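### The Kaplan-Meier plot of time to first dose reduction censors patients who stop LDK378 or die, so it does not show the probability that a treated patient is reduced

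*SAP*

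**What the plan says.** SAP 3.2.5 states: "Time to first dose reduction and time to first dose interruption will be presented graphically using Kaplan-Meier methodology". For reductions it adds: "Patients who did not have a dose reduction will be censored at the date of the last dose of study drug". It gives no censoring rule for time to first interruption.

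What the date of last dose means depends on the patient:

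- For a patient who has stopped, SAP 3.1.1.2 applies: "The date of last administration of study drug is defined as the last date when a non-zero dose of study drug is administered". Such a patient is censored at the moment of stopping.
- For a patient with no end-of-treatment page, no death date, and a last-dose date that is missing or after the cut-off, SAP 4.1.2.8 says: "the patient should be considered to be on-going and use the cutoff date for the analysis as the last dosing date". This is ordinary administrative censoring.

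No competing-risk method is named for this output. The same section also reports the number of patients with dose changes, reductions and interruptions with reasons, and summary statistics of the time to first event among patients who had one.

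**The concern.** A patient who has permanently stopped LDK378, or died, cannot have a later dose reduction. Censoring that patient treats them as still able to be reduced at the same rate as those who remain on drug. For the probability of being reduced, stopping is a competing event.

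Stopping is common here. The Protocol's Amendment 3 rationale reports that, as of 29-Sep-2015, "of 103 patients treated, 66 patients have been discontinued from treatment and 37 are still receiving study treatment". That is 66/103 = 64.1% off treatment, and this SAP serves the later final report.

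Stopping can also take the place of a reduction. Protocol Table 6-3 sends some toxicities directly to permanent discontinuation, for example any-grade treatment-related ILD/pneumonitis and grade 4 bilirubin. Some of the patients who tolerate the drug worst may therefore appear on the plot only as censoring marks.

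Safety and tolerability is a primary objective, so a reader may take this curve as a tolerability result and find that it disagrees with the crude count beside it.

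**Working it through.** The plan states no figure for this output, so there is nothing to reproduce. The check concerns direction first, then possible size.

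**Direction.** At a time with d reductions among n patients at risk:

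- one minus Kaplan-Meier rises by K × d/n, where K is the Kaplan-Meier value just before, which falls only at reductions;
- the Aalen-Johansen cumulative incidence rises by S × d/n, where S is the probability of neither reduction nor stop, which falls at both.

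S is never larger than K, so one minus Kaplan-Meier is never the lower of the two. The curves separate at the first reduction that follows an unreduced stop. For example, take 10 patients: one stops unreduced, then one of the remaining 9 is reduced. One minus Kaplan-Meier is 1/9 = 11.1%. The cumulative incidence is 0.9 × 1/9 = 10.0%, which matches the 1 in 10 actually reduced.

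Simulation agrees (n = 103, constant hazards, staggered cut-off, five scenarios of 1000 repetitions): one minus Kaplan-Meier was at or above the cumulative incidence every time. With monthly hazards of 0.10 for reduction and 0.05 for stopping, the 12-month means were 69.8% and 55.7%.

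**Size, as illustration only.** Let p be the cumulative incidence of reduction and q the share stopping without one, with common follow-up. Then:

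- lower bound: p, if all stops follow the last reduction;
- upper bound: p/(1 − q), if all stops precede the first reduction;
- proportional hazards: 1 − (1 − p − q)^(p/(p+q)).

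I set p = 0.584, borrowed from the earlier study (Protocol 1.2.1.2.1): "Dose reductions due to AEs occurred in 58.4% of patients treated with LDK378 at the 750 mg dose". The documents do not give q, so it is varied. One value, 10.2%, is the earlier study's share with AEs leading to discontinuation ("study drug discontinuations occurred in 10.2% of patients treated with LDK378 at the 750 mg dose"), which is not restricted to unreduced patients.

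| q (assumed) | Calculation under proportional hazards | 1 − KM | Bounds |
|---|---|---|---|
| 5% | 1 − 0.366^(0.584/0.634) | 60.4% | 58.4% to 61.5% |
| 10.2% | 1 − 0.314^(0.584/0.686) | 62.7% | 58.4% to 65.0% |
| 20% | 1 − 0.216^(0.584/0.784) | 68.1% | 58.4% to 73.0% |
| 30% | 1 − 0.116^(0.584/0.884) | 75.9% | 58.4% to 83.4% |

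**The other reading.** Suppose the target were the risk of reduction had nobody stopped. A simulation with a frailty shared by reduction and stopping gave one minus Kaplan-Meier 61.5%, cumulative incidence 50.8% and hypothetical risk 66.5%. Here Kaplan-Meier is too low, because the patients removed by stopping are those more likely to have been reduced.

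**The case against.** The strongest reply is that little depends on this plot. Protocol 10.5.3.5 says: "Tolerability will be summarized in terms of dose reductions or drug interruption due to an AE". That concerns AE-caused events, whereas the SAP 3.2.5 curve is not limited to them and sits among the exposure outputs. The AE-specific outputs are tabulations of AEs requiring dose adjustment or interruption (SAP 3.2.9.1). The curve is absent from both lists of first interpretable results (SAP 4.5.1 and 4.5.2) and from the interim figures in SAP Appendix 1, and no endpoint or decision uses it. This stands, and it sets the severity. A reader might infer that the primary tolerability result is wrong; the documents do not support that.

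A second reply is that the curve can be read as risk while on treatment, so overstatement depends on an estimand the SAP never states. This stands in part. The direction of error depends on the reading, but the SAP does not label the curve that way, and toxicity-related stopping would distort a nobody-stops reading too.

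A third reply is that crude counts already give the share reduced. They do, but they do not correct the curve printed beside them.

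A reader might also infer a gap of 12 to 25 percentage points at 12 months. That follows from taking 58.4% as reduction's share of all first events, with constant hazards and a median of 3 to 6 months to the first of reduction or stop (56%–80% against 44%–55%). The documents do not support it. The 58.4% is a crude share from another, ongoing study with median exposure 26.9 weeks, or 26.9 × 7/30.4375 = 6.19 months. At that time the model gives only 0.584 × (1 − 2^(−6.19/3)) = 44% or 0.584 × (1 − 2^(−6.19/6)) = 30%, so it misses its own input. The 3-to-6-month median has no source in the documents.

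**Conclusion.** The point holds, as a minor one. As the probability that a treated patient has had a dose reduction by time t, the planned curve cannot fall below the cumulative incidence and will generally exceed it, given how many patients have left treatment. It is not simply too high under every reading: for a hypothetical nobody-stops target it may be too low.

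The size cannot be derived from the documents, because the number of patients who stop without a prior reduction is not given. Under proportional hazards and an assumed incidence of 58.4%, the excess would be about 2 points at q = 5% (60.4 − 58.4), 4 at 10.2%, 10 at 20% and 18 at 30% (75.9 − 58.4 = 17.5). It is zero if every stop follows the last reduction. Patients still on treatment at the cut-off are censored correctly and add nothing to the problem.

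**What to change.** In SAP 3.2.5, replace the Kaplan-Meier plots by Aalen-Johansen cumulative incidence curves for both time to first dose reduction and time to first interruption. Code permanent discontinuation or death before the event as the competing event, and censor only patients still on treatment at the cut-off. For reductions the existing last-dose date can stay; only the status of patients who have stopped changes. Write the rule out for interruptions as well, since none exists now.

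This is a cheap improvement. The end-of-treatment and death information is already collected (SAP 3.2.4 and 3.2.9.1). The cost is two reprogrammed figures and some loss of comparability with the primary report: SAP 1.1 describes the method as similar to the primary-report plan apart from logged changes, and the document history logs no change to this rule. Showing the Kaplan-Meier version alongside, labelled as conditional on remaining on treatment, deals with that.
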